The sample size was calculated using standard estimate where n = 8(CV2) /(PC2) [1+(1-PC)2] where PC is the proportionate change in means (PC = $(\mu 0 - \mu 1)/\mu 0$) and CV is the coefficient of variation (CV = $\sigma 0/\mu 0 = \sigma 1/\mu 1$). The study required a minimum sample size of 33 (N) patients in each group. With an inflation of 40% for an estimated loss to follow up/non-response rate, we will be including 46 (N) participants in this study, to achieve 80% power and to detect at least a 39% change in mean canine retraction rate values of 3.88 ± 2.66 mm and 5.45 ± 1.53 mm, with

elastomeric power chains and Ni-Ti closed-coil springs, respectively⁸ and 68% or less change in coefficient of variation at two-sided 5% level of significance.

SAMPLE SELECTION:

Inclusion Criteria:

- Patients aged between 13 40 years
- Patients undergoing fixed orthodontic treatment
- Patients requiring all first premolars extraction as part of orthodontic treatment
- Patients with all permanent teeth present and erupted (except for second and third molars)
- All patients who will sign the informed consent/assent form

Exclusion Criteria:

- Patients with systemic diseases that can affect tooth movements
- Patients with uncontrolled periodontal disease
- Patients with craniofacial syndromes
- Pregnant or lactating mothers
- Patients with bracket failures greater than three times per bracket during the study
- Patients on medications that can affect tooth movements
- Patients with Nickel allergy

DATA COLLECTION PROCEDURE:

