Adverse events will be reported to ERC within a week and any serious adverse event will be reported to the Department of surgery, sponsors, CTU, DRC, and ERC within 24 hours. All emergency side effects will be managed in the emergency department and the Department of Surgery will bear the charges.

STUDY GROUPS:

The patients will be screened using the inclusion and exclusion criteria by the co-investigator. Measurements for the canine root resorption, retraction rate, plaque accumulation and gingival health will be taken at T_0 , T_1 , T_2 and T_3 .

Intervention: Ni-Ti closed-coil springs **Control:** Elastomeric power chains

The participants will receive routine instructions for oral hygiene maintenance and care of the appliance verbally.

MATERIAL STORAGE:

Ni-ti closed-coil springs and Elastomeric power chains will be stored at room temperature at the Department of Surgery, Dental inventory.

DATA ANALYSIS:

Data will be entered and analyzed in SPSS for Windows (version 23.0, SPSS Inc. Chicago). Frequencies and proportions will be reported for categorical variables, such as gender. Shapiro-Wilk test will be used to check the normality of the data. Descriptive statistics, such as means and standard deviations for normally distributed or median and interquartile range (IQR) for non-normally distributed data will be reported for all baseline clinical factors. Paired t-test will be used for the pairwise comparison. For the two groups the mean/median scores for retraction rate, root resorption, gingival health and plague accumulation between the two groups will be assessed using Independent t-test for normally distributed data and Man-Whitney U test for non-normally distributed data. A *p*-value ≤ 0.05 at 95% confidence interval will be considered as statistically significant.

On achieving 50% of the sample size, an interim analysis will be run, if the results show that the given intervention is successful in significantly improving the rate of canine retraction in patients then further trial will be stopped and all the participants will be given the intervention.

FINANCE:

Departmental funds from the Department of Surgery and intramural grants will be applied for.

PUBLISHING POLICY/PLAN:

For publication the data will be utilized, and it could be presented in either national or worldwide forums.

DATA CONFIDENTIALITY:

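### The trial can stop for efficacy at half the sample on ordinary significance and then tests again at p ≤ 0.05, so its rule does not secure the stated two-sided 5% level

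*Protocol*

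**What the plan says.** Four statements in the protocol bear on this point.

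- **Level claimed.** The Sample Size section plans for 80% power with "68% or less change in coefficient of variation at two-sided 5% level of significance".
- **Threshold.** The Data Analysis section gives one criterion, a p-value of at most "0.05 at 95% confidence interval will be considered as statistically significant".
- **Interim look.** The next paragraph of that section adds: "On achieving 50% of the sample size, an interim analysis will be run".
- **Stopping rule and consequence.** The trial ends early if the intervention is found "successful in significantly improving the rate of canine retraction in patients then further trial will be stopped". After such a stop, every patient in the study moves to the Ni-Ti springs.

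The protocol gives no separate interim p-value, spending function or reduced final level, and it does not refer to another document for one.

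**The concern.** Testing the primary outcome twice at the full 5% level gives two chances of a false positive. The interim sentence prints no p-value of its own, but it turns on significance, and the sentence just before that paragraph supplies the only definition of that word. Read as written, the trial spends 5% at the interim and 5% again at the end, while the sample size rests on 5% in total.

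Three things are at stake:

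- **The primary claim.** The error is tilted towards the intervention, because only a result in its favour triggers stopping. Investigators, patients and assessors are all unblinded, so a lenient early threshold has little other protection.
- **The size of the reported effect.** A trial that stops early on a low threshold reports, on average, an effect larger than the true one.
- **The secondary outcomes.** Stopping on retraction alone could leave root resorption, plaque and gingival health with about half the planned sample. The protocol does not say whether participants already enrolled would complete follow-up. The Rationale gives the scarcity of evidence on these same outcomes as a reason for the trial.

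**Working it through.** **Inputs from the protocol.** Two-sided level 0.05; one interim at information fraction 0.5; p ≤ 0.05 as the only threshold; means 3.88 and 5.45 mm; SDs 2.66 and 1.53 mm; 33 per group before inflation and 46 participants after it, so the interim falls at about 23.

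**Step 1. The plan's own figure.** The stated formula is n = 8·CV²/PC² × [1 + (1 − PC)²]. With CV = 0.68 and PC = 0.39:

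8 × 0.4624 / 0.1521 × (1 + 0.3721) = 33.4, which agrees with the stated 33. Then 33 × 1.40 = 46.2, which agrees with 46.

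The formula has no term for an interim look, so the sample size assumes a single test at 5%.

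**Step 2. Error with two looks.** Under no difference, the interim and final statistics (Z1, Z2) are bivariate normal with correlation √0.5 = 0.707. With critical value 1.960 at both looks:

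| Reading | Probability | Result | Nominal |
|---|---|---|---|
| Either direction counts at both looks | P(\|Z1\| > 1.96 or \|Z2\| > 1.96) | 0.083 | 0.05 |
| Only a Ni-Ti benefit stops the trial; final test two-sided | P(Z1 > 1.96 or \|Z2\| > 1.96) | 0.067 | 0.05 |
| False claim in favour of Ni-Ti | P(Z1 > 1.96 or Z2 > 1.96) | 0.042 | 0.025 |

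Simulated paired t-tests at 23 and 46 participants gave 0.083 to 0.085 for the first row and 0.066 to 0.068 for the second. If the interim falls at 40% or 60% of the information, the first row becomes 0.086 or 0.080.

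**Step 3. The independent t-test.** The plan names an independent t-test (or Mann-Whitney) for the between-group comparison, and a paired t-test only for an undefined pairwise comparison. On split-mouth data the independent t-test is conservative when the two sides correlate positively. The documents give no correlation r, so it is varied here as an assumption. Using the plan's SDs, the simulated two-look error of the independent t-test is approximately:

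| r | Either direction | Stop only for Ni-Ti |
|---|---|---|
| 0 | 8.5% | 6.7% |
| 0.1 | 7.0% | 5.6% |
| 0.2 | 5.6% | 4.5% |
| 0.3 | 4.3% | 3.4% |
| 0.5 | 1.9% | 1.4% |

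At r = 0.5 a single look with this test has an error of about 1.0%, so the second look still nearly doubles it on the either-direction reading.

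**Step 4. Estimate at an early stop (paired test, 23 pairs, p ≤ 0.05).** The SD of the within-patient difference is √(2.66² + 1.53² − 2r × 2.66 × 1.53), which is 2.31 mm at r = 0.5 and 3.07 mm at r = 0. Two true differences are considered: 0.5 mm, the 12-week figure quoted in the protocol's background, and the design difference, 5.45 − 3.88 = 1.57 mm.

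| True difference | r | Chance of stopping | Mean estimate when stopped | Ratio to truth | Chance of stopping at p < 0.0052 |
|---|---|---|---|---|---|
| 0.5 mm | 0.5 | 17% | 1.19 mm | 2.4 | 3% |
| 1.57 mm | 0.5 | about 87% | 1.68 mm | 1.07 | 57% |
| 1.57 mm | 0 | 65% | 1.92 mm | 1.22 | 29% |

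**Step 5. Boundaries that hold 5%.** Solving on the same bivariate normal distribution:

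- O'Brien-Fleming: z = 2.797 and 1.977, that is p = 0.0052 at interim and 0.0480 at the end.
- Haybittle-Peto: p = 0.001 at interim and 0.0498 at the end (an unadjusted 0.05 at the end would give 0.0502 overall).
- Pocock: z = 2.178, that is p = 0.0294 at both looks.

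**The case against.** The strongest objection is that the inflation is calculated for a paired test, whereas the plan names an independent t-test for comparing the groups. With that test the two-look error falls below 5% once r reaches about 0.3, or about 0.2 if only a Ni-Ti benefit stops the trial. The documents give no r, so it cannot be said that the error of the plan exactly as written exceeds 5%. This stands as a limit on the size. It does not make the rule sound: the error would depend on an unknown correlation, and once the test is matched to the split-mouth design the full inflation returns.

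The 2.4-fold exaggeration is also one scenario, with a small true effect. At the effect for which the trial is sized, the exaggeration is 1.07 to 1.22 times. That is correct, and both are shown above.

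Finally, the interim sentence prints no p-value, and a statistical analysis plan that is not shown might set a boundary. But the protocol itself fixes the look, its timing, the criterion and the consequence, and it gives one definition of significance. A later boundary would have to override what is written here.

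**Conclusion.** The concern holds. As written, the protocol allows the primary outcome to be declared significant at p ≤ 0.05 at half the sample and again at the end, and this does not secure the two-sided 5% level on which the trial is sized. With a correctly sized test and looks at 50% and 100%, the overall error is 6.7% on the closer reading and 8.3% if either direction counts. A false claim for Ni-Ti springs has a probability of 4.2% against 2.5%.

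These figures assume that significance at the interim means p ≤ 0.05 and that the test has correct size. With the independent t-test the two-look error could lie anywhere from about 8.5% to about 2% as r goes from 0 to 0.5. The exaggeration after an early stop depends on the true effect and on r, and is modest at the design effect. The point should be settled before any interim data are seen, because a boundary chosen afterwards would not be credible.

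**What to change.** State a group-sequential boundary for the retraction outcome in the Data Analysis section. Two options hold 5% overall:

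- **O'Brien-Fleming:** stop for efficacy only if two-sided p < 0.0052 at 50% of the sample; test at p < 0.048 at the end.
- **Haybittle-Peto:** p < 0.001 at interim and about 0.0498 at the end.

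Name the test to which the boundary applies, and make it one that respects the split-mouth pairing, since the thresholds control error only for a correctly sized test. State also that participants already randomised are analysed in their allocated arms. Alternatively, delete the efficacy interim; with three months of follow-up per patient and a one-year study, little is lost.

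The administrative cost is protocol wording. The statistical cost is a slightly stricter final threshold and a real fall in the chance of stopping early: with O'Brien-Fleming at the design effect, from about 87% to 57% at r = 0.5, or from 65% to 29% at r = 0.
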